Secondary Objectives	
 
• To demonstrate the benefit of canakinumab in reducing 4-week case fatality rate (CFR) among patients with COVID-19-induced pneumonia and CRS regardless of other subsequent clinical interventions
 
• To evaluate change from baseline in clinical serologic measurements related to CRS in COVID-19 patients with pneumonia
 
• To evaluate safety of canakinumab in patients with COVID-19-induced pneumonia and CRS
 

Study design	This is a Phase 3, multicenter, randomized, double-blind, placebo-controlled study to assess the efficacy and safety of canakinumab in patients with COVID-19-induced pneumonia and CRS. The study will enroll patients to canakinumab or placebo, in addition to standard of care per local practice, which may include anti-viral treatment, corticosteroids and/or supportive care. The total trial duration will be 126 days after the canakinumab or placebo dose. Safety will be closely monitored with an internal Novartis DMC during the study.

Study population	Approximately 450 patients with diagnosed COVID-19-induced pneumonia and CRS will be randomized to canakinumab or placebo in a 1:1 ratio
Key Inclusion criteria	
 
1. Male or female
 
2. Adults ≥ 18 years old (for US only: patients ≥ 12 years old)
 
3. Body weight ≥40 kg
 
4. Informed consent must be obtained prior to participation in this study. For US patients 12 - < 18 years old; parent/guardian consent must be obtained and assent if applicable.
 
5. Clinically diagnosed with SARS-CoV-2 virus by PCR or by other approved diagnostic methodology within 7 days prior to randomization
 
6. Hospitalized with COVID-19-induced pneumonia evidenced by chest x-ray or CT scan (taken within 5 days prior to randomization) with pulmonary infiltrates
 
7. SpO2 ≤ 93% on room air, or arterial oxygen partial pressure (PaO2)/fraction of inspired oxygen (FiO2) < 300mmHg (1mmHg=0.133kPa) (corrective formulation should be used for higher altitude regions (over 1000m))
 
8. C-reactive protein ≥20 mg/L or ferritin level ≥600 µg/L
 

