Key Exclusion criteria	
 
1. History of hypersensitivity to canakinumab or to biologic drugs
 
2. Intubated and on mechanical ventilation (invasive) at time of randomization
 
3. Treatment with immunomodulators or immunosuppressant drugs, including but not limited to tocilizumab, TNF inhibitors and anti-IL-17 agents within 5 half-lives or 30 days (whichever is longer) prior to randomization with the exception of anakinra which is excluded within 5 half-lives only. Note: Immunomodulators (topical or inhaled) for asthma and atopic dermatitis and corticosteroids (any route of administration) are permitted
 
4. Suspected or known untreated active bacterial, fungal, viral, or parasitic infection with the exception of COVID-19
 
5. Neutropenia with ANC <1000/mm^3
 
6. Any serious medical condition or abnormality of clinical laboratory tests that, in the investigator's judgment, precludes the patient's safe participation in and completion of the study
 
7. In the opinion of the investigator, progression to death is imminent and highly likely within the next 24 hours, irrespective of the provision of treatments
 
8. Current participation in any other investigational trials
 

Study treatment	
Arm 1: Canakinumab 450 mg for body weight 40-<60 kg, 600 mg for 60-80 kg, or 750 mg for >80 kg in 250 mL of 5% dextrose infused IV over 2 hours
 
Arm 2: 250 mL of 5% dextrose infused IV over 2 hours
 
Canakinumab or placebo infusions will be prepared and blinded by an unblinded pharmacist or designated staff member.

Treatment of interest	Randomized canakinumab or placebo as described above. In addition, all patients will receive SOC per local practice for the treatment of COVID-19-induced pneumonia. The SOC may include anti-viral treatment, corticosteroids and/or supportive care.

Efficacy assessments	
The WHO 9-point ordinal scale of clinical status will be assessed on a daily basis at baseline and after study treatment during hospitalization as well as on Days 15, 29, 57 and 127
 
[REDACTED]

[REDACTED]	[REDACTED]
[REDACTED]	[REDACTED]
Key safety assessments	
Adverse event monitoring, physical examinations, and monitoring of laboratory safety values.

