### **6.3.2 Treatment assignment, randomization**

At Randomization visit, all eligible patients will be randomized via IRT to one of the treatment arms. A designated site staff member (preferably the pharmacist conducting the blinding) other than the investigator or study staff involved in safety and efficacy assessments or eCRF completion will contact the IRT after confirming that the patient fulfills all the inclusion/exclusion criteria. The IRT will assign a randomization number to the participant, which will be used to link the participant to a treatment arm.

The randomization numbers will be generated using the following procedure to ensure that treatment assignment is unbiased and concealed from participants and investigator staff. A participant randomization list will be produced by the IRT provider, or by a delegate under Novartis supervision, using a validated system that automates the random assignment of participant numbers to randomization numbers. These randomization numbers are linked to the different treatment arms.

If a patient discontinues before Randomization, the IRT should be notified within two days and the reason for not being randomized should be recorded on the appropriate Case Report Forms.

Randomization will be stratified by country to ensure a balanced allocation of patients to treatment groups within the strata.

The randomization scheme for participants will be reviewed and approved by a member of the Randomization Office.

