## 2 Statistical methods.

### 2.1 Data analysis general information

For the primary analyses based on Day 29 DBL, efficacy analyses will be based on all data up to and including Day 29. The safety analyses will include all data up to the time of data cut (i.e., including data after Day 29 for those enrolled early in the study) if not otherwise specified.

At the final DBL, summary of all safety data collected from post treatment until end of study will be provided.

Novartis statistical and programming team will be performing the analyses as planned in this document. The Statistical Analysis System (SAS) 9.4 or higher versions will be used. R version 3.6.1 may also be used as appropriate.

Unless if otherwise clarified, descriptive summaries for categorical data will include frequencies and percentages, and continuous data will be presented with mean, standard deviation, median, minimum, and maximum. For selected parameters, geometric mean and geometric coefficient of variation (CV) may also be presented.

Rate differences and odds ratios (OR) for the comparisons between the two treatment arms will be presented with 2-sided 95% confidence interval (CI). P-values will be presented if formal hypothesis test is performed.

The randomization of the study is stratified by country to ensure a balanced allocation of patients to treatment groups within the strata. Statistical models will include adjustments for regions (North America and Europe) by pooling countries to regions. The countries are pooled by regions as follows:

North America: United States

Europe: Italy, France, Germany, Spain, United Kingdom, Hungary, Russia

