### 2.2.1 Subgroup of interest

Subgroup analyses will be conducted to assess consistency of the treatment effect among the subgroups without multiplicity adjustments. The following subgroups will be evaluated for the primary endpoint, i.e. survival without ever requiring invasive mechanical ventilation from Day 3 (inclusive) up to Day 29 (inclusive).

- Age category (< 65, ≥ 65 years)
- Age category (12 - <18; 18 - <40; 40 - <65; 65 - <75; ≥75)
- Baseline clinical status based on 9-point ordinal scale (≤4, ≥5)
- Baseline body Weight (40 kg - <60 kg, 60 kg – 80 kg, >80 kg)
- Baseline BMI categories (≤ 30.0 kg/m^2 and > 30.0 kg/m^2)
- Sex (male, female)
- Race (White, Asian, Black, other)
- Ethnicity: Hispanic, non-Hispanic
- Region (North America, Russia, Rest of Europe)
- Active comorbidities based on Medical History
  - Cerebrovascular disease (Yes, No)
  - Chronic heart disease (Yes, No)
  - Hypertension (Yes, No)
  - Diabetes (Yes, No)
  - Asthma (Yes, No)
  - COPD (Yes, No)
  - Chronic kidney disease (Yes, No)
  - Malignant neoplasm (Yes, No)
  - Liver disease (Yes, No)

- Use of dexamethasone >= 6 mg/day or equivalent or not (Yes, No)
- Use of remdesivir or not (Yes, No)
- Use of convalescent plasma/serum or not (Yes, No)
- Use of hydroxychloroquine or not (Yes, No)
- Use of azithromycin or not (Yes, No)
- Use of JAK inhibitor or not (Yes, No)
- Use of Heparin or not (Yes, No)

- Use of anti-IL6 treatment (Yes, No)

The subgroups based on the use of prior COVID-19-induced pneumonia treatment medication are defined as with/without the given medication that started on or after the onset of the first symptom of COVID-19-induced pneumonia and before the study treatment date (or randomization date if no study treatment is taken).

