### 2.6.2 Statistical hypothesis, model, and method of analysis

The null hypothesis for the key secondary analysis is that there is no difference in the COVID-19 related death rate (i.e. CFR) in patients treated with canakinumab compared to patients on placebo. The alternative hypothesis is that there is a difference between the two treatment groups.

The superiority of canakinumab over placebo will be concluded if the odds ratio  $<1$  for the COVID-19 related death between canakinumab and placebo and the null hypothesis can be rejected at the two-sided significance level of 0.05.

The test of the hypothesis will be based on a logistic regression model with study treatment, region (North America vs. Europe), baseline clinical status based on the 9-point ordinal scale ( $\leq 4, \geq 5$ ) as factors. Model-based estimates of the CFR and their 95% confidence intervals (CIs), estimate of the odds ratio and 95% CI, and p-value for comparing canakinumab vs. placebo will be provided. In case of model converge problem caused by separability, Firth's penalized maximum likelihood estimation will be performed based on the same logistic regression model. The estimated odds ratio, p-values and 95% CI (all computed by penalized profile likelihood) will be presented.

The number and percent of patients with COVID-19 related death during the 4-week period will also be summarized by treatment arms. The difference in observed response rates between canakinumab and placebo arms will also be presented along with the asymptotic 95% confidence interval.

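### Randomisation is stratified by country, but the visible tested models adjust only for North America versus Europe: the primary test stays valid, is slightly conservative, and gives up a little power

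*SAP*

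**What the plan says.** - **Randomisation.** Protocol 6.3.2: "Randomization will be stratified by country to ensure a balanced allocation of patients to treatment groups within the strata". SAP 1.1 and 2.1 repeat this.
- **Background care.** The Protocol summary gives both arms study treatment "in addition to standard of care per local practice, which may include anti-viral treatment, corticosteroids and/or supportive care".
- **Geographic covariate.** SAP 2.1: "Statistical models will include adjustments for regions (North America and Europe) by pooling countries to regions". The levels are "North America: United States" and "Europe: Italy, France, Germany, Spain, United Kingdom, Hungary, Russia", so eight countries become two levels, seven of them in one.
- **Key secondary model.** SAP 2.6.2 lists, besides treatment, "region (North America vs. Europe), baseline clinical status based on the 9-point ordinal scale". The marginal-standardisation sensitivity analysis in SAP 2.6.4 uses the same two levels.
- **Primary model.** Its text is redacted or not shown in Protocol 12.4.2 and in SAP 2.5.2 and 5.3.1. The covariates can be pieced together from elsewhere. The Protocol summary names treatment, region and baseline clinical status; SAP 2.1 defines region; SAP 5.3.2 says the key secondary analysis uses the primary model.
- **Subgroups.** SAP 2.2.1 splits geography three ways: "Region (North America, Russia, Rest of Europe").

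No visible text plans a country-adjusted analysis. Country itself appears only as a descriptive baseline item (SAP 2.3.2).

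**The concern.** Non-response includes needing invasive ventilation, which depends partly on local decisions and capacity. With background care also local, country may well predict outcome. That European countries differ in this way is an inference; the documents do not state it. But the sponsor chose country as the stratification factor, and the SAP does not treat Europe as uniform in its subgroup list.

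Stratified allocation removes between-country variation from the treatment comparison. A model that omits country still counts the within-Europe part of that variation as noise, so its standard error is somewhat too large. At stake is a little efficiency: the design arranges balance by country and the analysis does not use all of it.

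**Working it through.** **1. The plan's own power figure.** Inputs from SAP 3.1.1 and Table 3-1: 225 per arm, 50% versus 65%, two-sided 0.05. With a pooled-variance normal approximation:

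- SE under the null = √(2 × 0.575 × 0.425 / 225) = 0.0466
- SE under the alternative = √((0.50 × 0.50 + 0.65 × 0.35) / 225) = 0.0461
- z = (0.15 − 1.96 × 0.0466) / 0.0461 = 1.27, so power = 89.9%; the plan states 89%.

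The other primary rows give 89.3%, 91.0% and 94.8% (stated 89%, 90%, 94%). The key secondary rows give 92.7%, 84.6% and 71.3% (stated 92%, 83%, 70%). These calculations contain no region or country term, so this point does not challenge them.

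**2. Simulation of the primary model.** 4,000 trials per setting, 450 patients, eight countries, permuted blocks of 4 within country. Each trial was fitted with treatment + baseline status + two-level region, and again with country in place of region. Assumptions not in the documents: US share 45% or 25%; 40% of patients at baseline status 5 or worse, with log odds ratio −1; country effects within Europe with SD 0, 0.5 or 1.0 on the log-odds scale. Around a 50% response, SD 0.5 means European country rates of about 32% to 68%, and SD 1.0 about 18% to 82%. The power and odds-ratio columns use 50% versus 65%. Each cell is region model / country model.

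| US share | SD | Power % | Type I error % | Median OR |
|---|---|---|---|---|
| 45% | 0 | 91.8 / 91.8 | 5.5 / 5.6 | 1.93 / 1.95 |
| 45% | 0.5 | 92.2 / 93.0 | 4.3 / 4.6 | 1.94 / 2.00 |
| 45% | 1.0 | 92.1 / 93.7 | 4.2 / 5.5 | 1.92 / 2.09 |
| 25% | 0 | 92.3 / 92.5 | 5.0 / 5.1 | 1.93 / 1.95 |
| 25% | 0.5 | 92.2 / 93.0 | 4.9 / 5.5 | 1.94 / 2.01 |
| 25% | 1.0 | 94.8 / 96.5 | 3.3 / 4.6 | 1.98 / 2.22 |

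Monte Carlo SE is about 0.35 points for type I error and 0.4 for power. Power should be compared only within a row. Under the null, the median OR lay between 0.996 and 1.002 for both models. The power lost by the region model, from unrounded figures, is 0.8 points at SD 0.5 and 1.5 to 1.7 at SD 1.0.

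Two further simulations agree in direction. One omitted baseline status and used country shares of 35/20/10/10/10/5/5/5%. It gave 90.2% versus 91.0% at SD 0.5 and 91.8% versus 93.4% at SD 1.0. The other included baseline status and gave 92.3% versus 92.8% and 92.6% versus 94.0%, with type I error 4.0% versus 5.4% at SD 1.0.

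**3. Hand check of the conservatism.** At SD 0.5, seven equally weighted country rates of 0.32, 0.38, …, 0.68 have variance 0.0144, which is 5.8% of the binomial variance 0.25. If 55% of patients are in Europe, the unused share is 0.55 × 5.8% = 3.2%. The effective critical value is 1.96 / √(1 − 0.032) = 1.99, a true level of 4.6%. At SD 1.0 the variance is 0.0485 (19.4%), the unused share 10.7%, the critical value 2.07 and the level 3.8%. These approximations ignore baseline status and sit within Monte Carlo error of the simulated 4.3% and 4.2%.

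**4. Whether the death model can carry country.** At 15% versus 7.5% (SAP Table 3-2), expected deaths are 225 × (0.15 + 0.075) = 50.6. Treatment, baseline status and seven country terms make nine, or 5.6 deaths per term. Three-level region needs four terms, or 12.7 per term.

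A country with 5% of patients has 11.25 per arm, so P(no deaths) = (0.85 × 0.925)^11.25 = 0.067. For a 10% country it is 0.067² = 0.0045. With three of each, P(at least one country without deaths) = 1 − (1 − 0.067)³ × (1 − 0.0045)³ = 20%, before any country differences. Simulation with the 35/20/10/10/10/5/5/5% shares gave 21%, 36% and 67% at SD 0, 0.5 and 1.0; a separate run put the range at about 20% to 60%. The country model is separated in all such trials. The two-level model failed in none up to SD 0.5 and in about 1% at SD 1.0.

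**The case against.** The strongest case for leaving the plan alone has five parts.

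- **There is no validity problem.** This stands in full. A reader might infer from unadjusted country differences that the comparison is confounded or the error rate inflated. Allocation is balanced within country, the null odds ratio is 1.00, and the region model's type I error does not rise above nominal beyond Monte Carlo error.
- **The odds ratio is not biased.** This also stands. A reader might take the larger country-adjusted value as a correction. It is non-collapsibility: the models target different conditional odds ratios. At SD 0.5 the no-baseline simulation gave mean log ORs of 0.64 (region) and 0.67 (country). The plan's power table rests on a marginal OR of 1.86, log OR 0.62, to which the region model is the closer. The planned rate differences are unaffected.
- **The gain is small and rests on assumptions.** True. It is about a point at SD 0.5, and no passage supports the spread implied by SD 1.0. But with no spread at all, country adjustment cost no measurable power, so there is little to lose for the primary endpoint.
- **The protocol names region.** True for both tested analyses. Its visible text gives no levels, so three levels fit the wording; a full country factor does not, and SAP section 4 currently reports no change to these analyses.
- **Redaction may hide a country-based sensitivity analysis for the primary endpoint.** This cannot be ruled out.

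A reader might also see the separate Russia subgroup as a contradiction. It is not: that list is an exploratory check of consistency. It shows only that a finer split was thought worth making.

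**Conclusion.** The point holds as a small loss of efficiency. The visible tested models use a coarser factor than the one randomised on. For the primary endpoint this makes the test mildly conservative: at SD 1.0 type I error was 3.3% to 4.2% under the region model, while at SD 0.5 the effect is barely distinguishable from nominal. The cost is roughly 0.5 to 1 point of power at SD 0.5 and about 1.5 points at SD 1.0. The odds ratio lies about 3% below the country-conditional value at SD 0.5 and 8% to 11% below at SD 1.0, as a difference of target.

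These sizes rest on assumed country shares, between-country SD and baseline-status effect, and on the primary covariates as reconstructed around the redactions.

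A reader might infer that country should replace region in every tested model. The plan's own death rates do not support that: a full country factor would often be separated, so the Firth fallback would become a common path.

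**What to change.** 1. **Primary analysis (SAP 2.1 and the primary model).** Adjust for country as randomised. Pool small countries by a rule based only on enrolment counts and fixed before unblinding. Do not pool on observed events, because the tested model would then depend on the outcome.
2. **Sensitivity analysis.** Keep the two-level region model for the primary endpoint.
3. **Key secondary death model (SAP 2.6.2).** Do not use the full country factor. Use at most the three levels in SAP 2.2.1 (North America, Russia, Rest of Europe), with the Firth fallback already specified. SAP 5.3.2 says this model is the same as the primary one and would need rewording.
4. **Documentation.** Record the change in SAP section 4 and amend the protocol if needed, since Protocol 14.1 requires a written amendment for any change to it.

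The cost is a few more model terms, SAP text settled before the Day 29 lock, and a documented departure from the two-level region definition, in return for a small gain.

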#### 2.1.1 General definitions

##### Study treatment

This is a one-time treatment study. Study treatment refers to canakinumab (including patients on any dose as per [Table 2-1](#)) in 250 mL of 5% dextrose infused IV over 2 hours or placebo as 250 mL of 5% dextrose infused IV over 2 hours.

**Table 2-1 Canakinumab dose by body weight**

Patient's weight (kg)	Dose of canakinumab	Volume of 150 mg/mL
> 80	750 mg	5.0 mL
60 to 80	600 mg	4.0 mL
40 to < 60	450 mg	3.0 mL

##### Study day

Day 1 is defined as the date when the study treatment is started. Study day is defined as the number of days since the date of study treatment (Day 1).

Therefore, for a particular date, study day will be calculated as follows:

- for dates on or after Day 1:  
Study day = Assessment date – Day 1 + 1;
- for dates prior to Day 1:  
Study day = Assessment date – Day 1.

If a patient never took any double-blind treatment, the randomization date will be used as Day 1.

### **2.1.1.1      Baseline**

The baseline value is defined as the last assessment performed prior to start of study treatment at Day 1.

For patients who are not treated, the baseline is the last assessment scheduled for pre-baseline visit on or before the randomization date, e.g., a 9-point ordinal scale on Day 1 pre-dose visit is considered as baseline.

### **2.1.1.2      Post-baseline measurement**

All data collected after the start of study treatment are defined as post-baseline. For patients who are not treated, the post-baseline is any scheduled post-baseline assessments on or after the randomization visit, e.g., a 9-point ordinal scale on Day 1 or an assessment for early exit visit on the randomization date is considered post-baseline measurement.

The following formula will be used, depending on how the post-baseline endpoint is defined, for each scheduled visit and time-point where baseline and post-baseline values are both available:

Change from baseline = post-baseline value – baseline value.

Percent change from baseline = (post-baseline value – baseline value)/baseline value\*100%.

Ratio to baseline = post-baseline value / baseline value.

AEs will be considered as treatment-emergent if the event is starting after the start of double-blind treatment or the event is present prior to start of double-blind treatment but increased in severity after the start of treatment based on preferred term and up to end of study on Day 127.

Details on calculation of post-baseline values are provided in the latter sections.

### **2.1.1.3      End of study/end of treatment**

The end of study (EoS) date is the date when a patient completes or discontinues the study, i.e., the “Disposition Event Date” from the “disposition” CRF form for study disposition.

This is a one-time treatment study and disposition status based on the study treatment is not applicable.

For reporting data by visit in outputs, the discontinuation from study visit will be allocated to the visit number based on the day of EoS if discontinuation is on or before Day 29. For the

assessments that are scheduled on every other day and EoS visit falls on a day without scheduled assessment, the EoS visit will be mapped to next scheduled visit for the corresponding assessment. If the discontinuation from study is after Day 29, the EoS visit will be mapped to the next scheduled visit.

